6. STUDY POPULATION ANALYSES

6.1. Overview of Planned Analyses

[Table 4](#) and [Table 5](#) and provide an overview of the planned study population displays, with full details of data displays being presented in [Appendix 10: List of Data Displays](#).

The study population listings and summaries will be based on the Safety population unless otherwise specified in [Appendix 10: List of Data Displays](#).

Table 4 Overview of Study Population Summaries (Part A)

Endpoint / Parameter	Data Displays Generated		
	Table	Figure	Listing
Subject Disposition			
Analysis populations	Y ^[1]		
Reasons for screen or run-in failures	Y		Y
Failed inclusion/exclusion criteria for screen or run-in failures	Y		
Failed inclusion/exclusion criteria for Safety Population	Y		Y
Subjects by country and site	Y		
Reason for premature study withdrawal	Y		Y
Demographic and Baseline Characteristics			
Demographic characteristics	Y		Y
Age Ranges	Y		
Race and racial combinations	Y		Y ^[3]
Race and racial combinations details	Y		
Medical Conditions			
Past medical conditions	Y		
Current medical conditions	Y		
Cardiovascular assessments (family history)	Y		
Baseline Disease Characteristics			
Asthma exacerbation history ^[2]	Y		
Asthma history and baseline disease characteristics	Y		
Lung function results (screening and baseline)	Y		
Prior and concomitant medications			
Asthma concomitant medications (taken before/during run-in, during treatment, post-treatment) by Respiratory Medication Class ^[4]	Y		
Non-asthma concomitant medications taken during treatment	Y		
Relationship between ATC level 1, Ingredient and verbatim text			Y
Protocol deviations			
Important protocol deviations	Y		Y

NOTES :

- Y = Yes display generated.
- [1] To include summary of subjects moving into study Part B
- [2] Asthma exacerbation recorded in 12 months prior to Screening
- [3] Listing of race
- [4] Multi-ingredient medications will be presented according to their combination Anatomical Therapeutic Chemical (ATC) classification rather than the classification of the ingredients.

Table 5 Overview of Study Population Summaries (Part B)

Endpoint / Parameter	Data Displays Generated		
	Table	Figure	Listing
Subject Disposition			
Analysis Populations	Y		
Reason for premature study withdrawal	Y		Y
Prior and concomitant medications			
Asthma concomitant medications (during treatment, post-treatment) by Respiratory Medication Class ^[1]	Y		
Non-Asthma concomitant medications taken during treatment	Y		
Relationship between ATC level 1, Ingredient and verbatim text			Y
Protocol deviations			
Important Protocol Deviations	Y		Y

NOTES :

- Y = Yes display generated.
- [1] Multi-ingredient medications will be presented according to their combination Anatomical Therapeutic Chemical (ATC) classification rather than the classification of the ingredients.

7. PRIMARY ANALYSES

This section contains the details of the planned primary Pharmacokinetic (PK) and Pharmacodynamic (PD) analyses using the study populations defined in Section 4. If there are protocol deviations that are thought to potentially impact the primary PK and/or PD endpoints, an exploratory sensitivity analysis may be considered. Any sensitivity analyses performed will be documented in the clinical study report.

All safety analyses are detailed within Section 8.2.

Full details of data displays are presented in [Appendix 10: List of Data Displays](#).

Table 6 Overview of Planned Primary Analysis (Part A)

Endpoint / Parameter/ Display Type]	Untransformed							Log-transformed						
	Pop-PK model			Summary		Individual		Stats Analysis			Summary		Individual	
	T	F	L	T	F	F	L	T	F	L	T	F	F	L
PK														
PK Plasma Concentrations (Observed and Predicted)				Y	Y ^[1]	Y ^[2]	Y							
Individual PK Parameter Estimates (also called post-hoc individual PK parameter estimates)				Y			Y				Y			
Population PK parameter estimates	Y													
Goodness of fit test/plots	Y	Y												
Endpoint / Parameter/Display Type]	Raw Data							Ratio of Post Dosing Visit to Baseline						
	Stats Analysis			Summary		Individual		Stats Analysis			Summary		Individual	
	T	F	L	T	F	F	L	T	F	L	T	F	F	L
Blood Eosinophil Count														
Blood Eosinophil Count (Part A)				Y	Y		Y				Y	Y		

NOTES :

- T = Table, F = Figure, L = Listing, Y = Yes display generated.
- Stats Analysis = Represents TFL related to any formal statistical analyses (i.e. modelling) conducted.
- Summary = Represents TFL related to any summaries (i.e. descriptive statistics) of the observed raw data/predicted data.
- Individual = Represents FL related to any displays of individual subject (observed raw data/predicted data).

^[1] Model Predicted Mepolizumab Individual Plasma Concentration Time Profiles with Individual Observed Plasma Concentrations and Plasma Concentration Population Prediction from Final Model by Treatment

^[2] Model Predicted Mepolizumab Individual Plasma Concentration Time Profiles with Individual Observed Plasma Concentrations and Plasma Concentration Population Prediction from Final Model by Subject

7.1. Population PK Analysis (Part A)**7.1.1. Overview of Planned Population PK Analysis**

This study is conducted to support the extrapolation of the safety and efficacy data observed in adults in the Phase III Mepolizumab Programme to the paediatric population. To this purpose, one of the PK objectives of the study is to characterize the pharmacokinetics of mepolizumab administered subcutaneously to subjects aged 6 to 11 years old with severe eosinophilic asthma.

A sparse PK sampling scheme has been implemented in this study and the PK samples collected will be analysed by population PK methods, using appropriate software, and based on the PK population defined, unless otherwise specified. All subjects who are in the PK population, i.e. who have at least one measurable PK concentration recorded, will

be included in this analysis. In order to model the paediatric data collected, a number of pharmacokinetic parameters in the model will be fixed using adult values because of the sparse sampling implemented in this paediatric study and the relatively small sample size selected. In particular estimation of absorption and distribution parameters is unlikely to be meaningful based on the proposed sampling scheme.

A description of the key models tested during the model development will be provided and tabulated. The population PK parameter estimates (AUC(0-inf), clearance, C_{max} and t_{1/2}) with 95% CI from the final model will be tabulated (for mepolizumab overall (Mepolizumab SC)). Goodness of fit plots for the final model will be presented.

Additionally, the individual PK parameter estimates (also called model-predicted post-hoc individual PK parameter estimates) for AUC_(0-inf), clearance, C_{max} and t_{1/2} as well as the individual observed and predicted plasma PK concentrations will be listed and summarised by mepolizumab dose and mepolizumab overall using descriptive statistics. The summary of the model-predicted post-hoc individual PK parameter estimates will include summary statistics for untransformed and log_e-transformed data. See details of the summary statistics in Section 10.5.3.

A summary of plasma concentration data will be produced only including summary statistics for untransformed data. Observed and model predicted concentrations will be presented graphically by treatment and subject. Furthermore, a plot of model predicted (5th, 50th, and 95th Percentiles) mepolizumab plasma concentrations with individual observed plasma concentrations for the final PK model for model evaluation will be generated.

In support of the described analysis, a specific dataset will be generated. Further details of the population PK analysis are provided in [Appendix 8: Population Pharmacokinetic Analyses](#).

Any subjects and/or PK concentration excluded from this analysis will be flagged in the data listings and documented in the clinical study report.

7.2. Analysis of Blood Eosinophil Count (Part A)

The blood eosinophil count (primary PD endpoint in this study) is recorded during the laboratory investigations under hematology data at the visits indicated in the [Appendix 2: Time & Events](#). Week 12 is the primary timepoint of interest for blood eosinophil count and ratio of blood eosinophil count to baseline.

The absolute blood eosinophil count, and ratio to baseline will be summarised using geometric mean and other descriptive statistics and listed for each mepolizumab dose and overall by visit for the PDe population. Additionally the geometric mean ratio to baseline in blood eosinophil count (including 95% CI) for each mepolizumab dose and overall by visit will be presented graphically. See details of the summary statistics in Section 10.5.3.

8. SECONDARY ANALYSES

8.1. Secondary and Exploratory Analyses

Table 7 provides an overview of the planned analysis of secondary and exploratory endpoints with further details of data displays being presented in Appendix 10: List of Data Displays.

All safety analyses are detailed within Section 8.2.

Table 7 Overview of Planned Secondary and Exploratory Analyses

Endpoint / Parameter/Display Type]	Raw Data								Change from Baseline							
	Stats Analysis			Summary		Individual			Stats Analysis			Summary		Individual		
	T	F	L	T	F	F	L	T	F	L	T	F	F	L		
Secondary Endpoints																
Part A																
Body-weight-adjusted clearance				Y												
ACQ-7 score				Y							Y	Y				
C-ACT score				Y							Y	Y				
Part B																
Blood Eosinophil Count				Y	Y		Y				Y ^[1]	Y ^[1]				
Exploratory Endpoints																
Part A																
ACQ-7 responder/non-responder category											Y					
ACQ-5 score				Y							Y	Y				
ACQ-5 responder/non-responder category											Y					
FEV ₁				Y							Y	Y				
Overview of Exacerbations				Y												
Exacerbations (on-treatment) (Week 0 – Week 12)				Y												
Exacerbations (on- and post-treatment) (Week 0 – Week 20)				Y			Y									
Time to first exacerbation (Week 0 – Week 20)				Y ^[2]								Y ^[2]				
Total IgE				Y							Y ^[1]					
Total IL-5				Y			Y				Y ^[1]	Y ^[1]				
PK Plasma Concentrations (Observed and Predicted)					Y ^[3]	Y ^[4]										
PK model goodness of fit test/plots	Y	Y														

Endpoint / Parameter/Display Type]	Raw Data							Change from Baseline						
	Stats Analysis			Summary		Individual		Stats Analysis			Summary		Individual	
	T	F	L	T	F	F	L	T	F	L	T	F	F	L
PKPD Plasma Concentrations (Observed and Predicted)					Y ^[3]	Y ^[4]								
PKPD model goodness of fit test/plots	Y	Y												
Part B														
ACQ-7 score				Y							Y			
ACQ-7 responder/non-responder category											Y			
ACQ-5 score				Y							Y			
ACQ-5 responder/non-responder category											Y			
C-ACT score				Y							Y			
FEV ₁				Y							Y			
Overview of Exacerbations				Y										
Exacerbations (on-treatment) (Week 20 – Week 72)				Y			Y							
Time to first exacerbation (Week 20 –Week 72)				Y ^[2]										

NOTES :

- T = Table, F = Figure, L = Listing, Y = Yes display generated.
- Stats Analysis = Represents TFL related to any formal statistical analyses (i.e. modelling) conducted.
- Summary = Represents TFL related to any summaries (i.e. descriptive statistics) of the observed raw data/predicted data.
- Individual = Represents FL related to any displays of individual subject (observed raw data/predicted data).

^[1] To be presented as a Ratio to Baseline

^[2] Kaplan-Meier estimates

^[3] Model Predicted Mepolizumab Individual Plasma Concentration Time Profiles with Individual Observed Plasma Concentrations and Plasma Concentration Population Prediction from Final Model by Treatment

^[4] Model Predicted Mepolizumab Individual Plasma Concentration Time Profiles with Individual Observed Plasma Concentrations and Plasma Concentration Population Prediction from Final Model by Subject

8.1.1. Body-Weight-Adjusted Clearance

The secondary PK objective of the study is to compare the bodyweight-adjusted clearance in this study from subjects aged 6 to 11 years old with historical values for adults with severe eosinophilic asthma when mepolizumab is administered subcutaneously. To this purpose, the point estimate for the bodyweight-adjusted clearance parameter derived as part of the primary objective (Section 7) will be presented in an additional table with a 90% CI. This point estimate and 90% CI for subjects aged 6 to 11 years will be compared with the historic adult estimated body-weight adjusted clearance of 0.22 L/day (corresponding to an apparent clearance of 0.29 L/day assuming

an absolute bioavailability of 75%), around which a proposed 80-125% interval was applied i.e. 0.18-0.28 L/day. The historic adult value is based on previous estimates obtained in studies conducted in adult subjects with severe eosinophilic asthma (i.e. 0.22 L/day as analysed in study MEA115588 [GSK Document Number: [2013N178278_02](#)] adjusted for an estimated bioavailability of 75%).

8.1.2. Asthma Control Questionnaire

The ACQ-7 score (mean of 7 items) and change from baseline in ACQ-7 score will be summarised by visit, mepolizumab dose and mepolizumab overall for the PDo population. For an overview of the ACQ-7 questionnaire and scoring algorithm please refer to Section [10.6.5](#).

The ACQ-5 score (mean of 5 symptom items) and change from baseline in ACQ-5 score will be summarised by visit, mepolizumab dose and mepolizumab overall for the PDo population. For an overview of the ACQ-5 questionnaire and scoring algorithm please refer to Section [10.6.5](#).

8.1.3. Childhood Asthma Control Test (C-ACT)

The C-ACT score (sum of 7 items) and change from baseline in C-ACT score will be summarised by visit, mepolizumab dose and mepolizumab overall for the PDo population. For an overview of the C-ACT questionnaire and scoring algorithm please refer to Section [10.6.5](#).

8.1.4. Analysis of Blood Eosinophil Count (Part B)

The absolute blood eosinophil count and ratio of blood eosinophil count to baseline will be summarised using descriptive statistics and listed for each mepolizumab dose and overall by visit for the PDe population as presented within Part A (See Section [7.2](#)).

The same baseline definition (latest value recorded prior to the first dose of mepolizumab in Part A) will be used in the analyses of both Part A and Part B data, as described within Section [10.5.2](#).

8.1.5. Forced expiratory volume in 1 second (FEV₁)

FEV₁ recorded at post-dose visits and change from baseline will be listed and summarised by mepolizumab dose group and mepolizumab overall for each visit.

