2.2.2. Pharmacokinetics of mepolizumab

Mepolizumab is a humanized IgG1 monoclonal antibody (mAb) that exhibits dose-proportional and time-independent pharmacokinetics. After SC administration to adults and adolescents mepolizumab is absorbed slowly, with an absolute bioavailability in the arm of 74–80% and median time to maximum concentration (T_{max}) values ranging from 4–8 days. Mepolizumab distributes into a central volume of distribution (V_c) similar to plasma volume with a distribution half-life of 1–2 days, and has a steady-state volume of distribution (V_{ss}) of 1.5–2 times plasma volume (55–85 mL/kg). Mepolizumab is catabolized by ubiquitous proteolytic enzymes, not restricted to hepatic tissue, and is cleared slowly with a terminal-phase elimination half-life of approximately 20 days, irrespective of the route of administration, and mean systemic clearance (CL) of 1.9–3.3 mL/day/kg. Mepolizumab does not undergo target-mediated clearance. When dosed every four weeks, mepolizumab shows two-fold steady-state accumulation, irrespective of route of administration, consistent with the terminal-phase elimination half-life of 20 days.

The pharmacokinetics of IV mepolizumab are well-described using a two-compartment model with first-order distribution and elimination and the population PK parameter estimates consistent across analyses. Although bodyweight was found to have a statistically significant effect on both clearance and volume, the overall magnitude of the effect of body weight on mepolizumab exposure was not deemed clinically relevant. The pharmacokinetics of mepolizumab is consistent across studies, diseases and ethnicities, with pediatric pharmacokinetics predictable from adults. Of note, a previous study was conducted with mepolizumab IV in pediatric subjects 2–17 years old with eosinophilic esophagitis ([Assa'ad](#), 2011). After adjusting for bodyweight via weight-based dosing, age was not a determinant of exposure. A population PK analysis of the data using the previous adult meta-analysis IV model described the data adequately without parameter

estimation or bias, implying that adult pharmacokinetics, estimated from multiple studies, diseases and populations, predicts pediatric pharmacokinetics.

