Bodyweight	X	X ¹	X ¹	X ¹	X ¹	X ¹	X ¹	X ¹	X ¹	X ¹	X ¹	X ¹	X ¹				
Adverse events	X	X	X	X	X	X	X	X	X	X	X	X	X	X	X	X	
Cardiovascular events	X	X	X	X	X	X	X	X	X	X	X	X	X	X	X	X	
Liver events	X	X	X	X	X	X	X	X	X	X	X	X	X	X	X	X	
Laboratory Assessments²																	
Urinalysis	X ¹					X								X		X	
Pregnancy Test	U	U	U	U	U	U	U	U	U	U	U	U	U	U	U	U	
Blood sample for immunogenicity ²							X						X		X	X	
Outcomes Assessments																	
FEV1	X ¹			X			X			X			X	X	X	X	
ACQ-7	X ¹			X			X			X			X	X	X	X	
C-ACT	X ¹			X			X			X			X	X	X	X	

Procedure	Eligibility Check / First Dose	Treatment Period												Exit Visit	Follow-up ³	Early Withdrawal
Visit	9	10	11	12	13	14	15	16	17	18	19	20	21	22	23	
Week of Study (visit window \pm 5 days)	20	24	28	32	36	40	44	48	52	56	60	64	68	72	80	
Assessment of exacerbation	X	X	X	X	X	X	X	X	X	X	X	X	X	X	X	X
Investigational Product																
Mepolizumab SC dose administered	X	X	X	X	X	X	X	X	X	X	X	X	X			
Study Administration																
Email to GSK Operational Lead	X	X	X	X	X	X	X	X	X	X	X	X	X	X	X	X
Complete eCRF	X	X	X	X	X	X	X	X	X	X	X	X	X	X	X	X

1. Bodyweight will be measured at Visit 9 and at each visit until such time as the subject reaches 40kg in weight. Subjects with bodyweight \geq 40Kg at Visit 9 will not be weighed again during Part B.
2. All laboratory samples should be collected prior to the administration of study medication
3. The 12-week post-dose follow-up visit (Visit 23) is not required for subjects transitioning to the long-term access program.

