2.1. Changes to the Protocol Defined Statistical Analysis Plan

Any changes from the originally planned statistical analysis specified in the protocol amendment 4 (dated 05/MAY/2016) are outlined in [Table 1](#).

Table 1 Changes to Protocol Defined Analysis Plan

Protocol	Reporting & Analysis Plan	
Statistical Analysis Plan	Statistical Analysis Plan	Rationale for Changes

 • Part B endpoint listed as 'Change from Week 20 (Visit 9) in absolute blood eosinophil count at weeks 32, 44, 56, 68, 72 and 80' 	
 • Part B endpoint listed as 'Change from Baseline in absolute blood eosinophil count at weeks 32, 44, 56, 68, 72 and 80' 	
 • Patients will not have returned to their pre-mepolizumab treatment baseline at the start of part B [Week 20 (Visit 9)] and therefore individual patient comparisons back to Baseline (Week 0) are more of interest

 • Part B endpoint listed as 'Change from Week 20 (Visit 9) in ACQ-7 and C-ACT at weeks 32, 44, 56, 68, 72 and 80.' 	
 • Part B endpoint listed as 'Change from Baseline in ACQ-7 and C-ACT at weeks 32, 44, 56, 68, 72 and 80.' 	
 • Patients will not have returned to their pre-mepolizumab treatment baseline at the start of part B [Week 20 (Visit 9)] and therefore individual patient comparisons back to Baseline (Week 0) are more of interest

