10.5.2. Baseline Definition & Derivations**10.5.2.1. Definition of Baseline**

- The baseline value for each assessment will be the latest value recorded prior to the first dose of mepolizumab.
- If an assessment was performed on the same day as the first dose of study treatment but it is known that the assessment was done after administration of treatment (i.e. because time of assessment is available and is after time of first dose) then this value will not be used as the baseline value.
- The same baseline definition (latest value recorded prior to the first dose of mepolizumab in Part A) will be used in the analyses of both Part A and Part B data.

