10.5.2.2. Derivations of Change from Baseline Data

Definition	Reporting Details
Change from Baseline	= Post-Dose Visit Value – Baseline
Ratio to baseline	= Post-Dose Visit Value / Baseline
Maximum Change from Baseline	= Highest Post-Dose Value - Baseline

NOTES :

- Unless otherwise specified, the baseline definitions specified in Section 10.5.2.1 will be used for derivations for endpoints / parameters and indicated on summaries and listings.
- The baseline definition will be footnoted on all change from baseline displays.

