10.10.3.2. Efficacy Tables

No.	Population	IDSL / TST ID / Example Shell	Title	Programming Notes	Deliverable [Priority]
Blood Eosinophil Count					
2.25.	PDe		Summary of Blood Eosinophil Count (Part B)	Log transformed with geometric mean, include ratio to baseline See format of Efficacy Table 2.73 (200862 'final' reporting effort) To also include 95% CIs by visit	SAC
Asthma Control Questionnaire					
2.26.	PDo		Summary of ACQ-7 Score (Part B)	See format of Efficacy Table 2.34 (200862 'final' reporting effort) To also include 95% CIs by visit	SAC
2.27.	PDo		Summary of 0.5 Point or More Reduction in ACQ-7 Score from Baseline (Part B)	See format of Efficacy Table 2.41 (200862 'final' reporting effort). Note: Logistic regression to not be included and Odds Ratio to not be shown	SAC
2.28.	PDo		Summary of ACQ-5 Score (Part B)	See format of Efficacy Table 2.34 (200862 'final' reporting effort) To also include 95% CIs by visit	SAC
2.29.	PDo		Summary of 0.5 Point or More Reduction in ACQ-5 Score from Baseline (Part B)	See format of Efficacy Table 2.41 (200862 'final' reporting effort). Note: Logistic regression to not be included and Odds Ratio to not be shown	SAC

No.	Population	IDSL / TST ID / Example Shell	Title	Programming Notes	Deliverable [Priority]
Childhood Asthma Control Test (C-ACT)					
2.30.	PDo		Summary of C-ACT Score (Part B)	See format of Efficacy Table 2.34 (200862 'final' reporting effort) To also include 95% CIs by visit	SAC
FEV1					
2.31.	PDo		Summary of FEV ₁ (Part B)	See format of Efficacy Table 2.27 (200862 'final' reporting effort) To also include 95% CIs by visit	SAC
Asthma Exacerbations					
2.32.	PDo		Overview of Asthma Exacerbations (Part B)	See format of Efficacy Table 2.61 (200862 'final' reporting effort).	SAC
2.33.	PDo		Summary of Frequency of Exacerbations (Week 20 –Week 72) (Part B)	See format of Efficacy Table 2.62 (200862 'final' reporting effort)	SAC
2.34.	PDo		Summary of Time to First Asthma Exacerbation (Part B)	See format of Efficacy Table 2.68 (200862 'final' reporting effort)	SAC

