10.11. Appendix 11: Example Mock Shells for Data Displays

See Supplementary RAP material

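### Part B FEV1 change from Week 0 has no stated height or age adjustment and no control arm, so growth alone could look like lung-function gain

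*SAP*

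**What the plan says.** SAP 8.1.5 covers both study parts in one sentence: FEV1 "recorded at post-dose visits and change from baseline will be listed and summarised by mepolizumab dose group and mepolizumab overall for each visit". SAP Table 7 repeats this for Part B under exploratory endpoints. Table 2.31 (SAP 10.10.3.2) implements it, with the programming note "See format of Efficacy Table 2.27 (200862 'final' reporting effort) To also include 95% CIs by visit". The mock shells are not in the SAP; Appendix 11 reads only "See Supplementary RAP material".

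SAP 10.5.2.2 defines change from baseline as "Post-Dose Visit Value – Baseline". On the baseline, SAP 10.5.2.1 states: "The same baseline definition (latest value recorded prior to the first dose of mepolizumab in Part A) will be used in the analyses", and it applies this to both parts. Part B spirometry is scheduled at Weeks 20, 32, 44, 56, 68, 72 and 80 (protocol Table 4), with the limit that "The 12-week post-dose follow-up visit (Visit 23) is not required for subjects transitioning to the long-term access program".

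SAP 10.6.2 defines GLI-2012 percent predicted FEV1, but as a disease parameter under study population. No by-visit FEV1 display is assigned it. By visit it appears only as one of the seven ACQ-7 items (SAP 10.6.5).

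**The concern.** FEV1 in litres or millilitres rises as a child grows taller. A raw difference from Week 0, followed for well over a year in children aged 6 to 11 at entry, therefore mixes any treatment effect with growth. There is no control arm to separate the two. A positive mean change with a CI that excludes zero could be read as sustained improvement in lung function when part or all of it is growth.

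The dose-group columns add to the difficulty. SAP 10.5.1.2 reports children who switch from 40 to 100 mg in Part B as a separate group, and they switch because their bodyweight reaches 40 kg. That group is defined by body growth, so if height follows weight, a comparison of raw FEV1 change across groups is confounded with growth.

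**Working it through.** The plan gives no sample size, SD or effect size for FEV1, so it has no figure to reproduce.

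**Scale of the table.** SAP 8.1.5 refers to FEV1 as recorded, and the title of the parallel Part A Figure 2.21 gives mL. Both point to raw volume. Table 2.31 itself states no unit.

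**Elapsed time.** Week 72 is 72 × 7 = 504 days, or 504/365.25 = 1.38 years. Week 80 is 560 days, or 1.53 years. Week 12, the only FEV1 endpoint time in the protocol, is 84 days, or 0.23 years.

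**Size of the growth drift (illustration).** None of these inputs is in the documents; all are assumptions:
- starting height and FEV1: 120 cm and 1.3 L, 135 cm and 1.6 L, or 145 cm and 2.0 L
- growth g: 4, 5 or 6 cm/year
- FEV1 proportional to height to the power k: 2.0, 2.3 or 2.6

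Change from growth alone = baseline × [((H + g × weeks/52)/H)^k − 1].

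Central case at Week 72 (135 cm, 1.6 L, 5 cm/year, k = 2.3): height gain 5 × 72/52 = 6.92 cm; (141.92/135)^2.3 − 1 = 0.122; 0.122 × 1600 mL ≈ 195 mL.

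| Visit | Range, mL | Range, % | Central, mL |
|---|---|---|---|
| Week 12 | 20–50 | 1.3–3.0 | 32 |
| Week 20 | 34–84 | 2.1–5.1 | 53 |
| Week 72 | 123–312 | 7.8–19.0 | 195 |
| Week 80 | 137–348 | 8.7–21.2 | 217 |

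Wider assumptions (120–140 cm, 4–7 cm/year, k from 2 to 3, starting FEV1 1.2–2.0 L) give 8% to 26% at Week 72, with a middle case of 15%, and 1% to 4% at Week 12. The size moves with the assumptions; the upward direction, increasing with time, does not. Protocol 2.2.1 cites progressive loss of lung function in severe childhood asthma, so the drift may be smaller here. At half of normal growth the Week 72 range is 62 to 156 mL.

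**Would the CI exclude zero?** The half-width is SD × t(0.975, n−1)/√n. The multiplier is 1.049 at n = 6, 0.468 at n = 20 and 0.388 at n = 28. Dividing the drift by the multiplier gives the SD of change below which growth alone would give a CI above zero:

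| Assumed n | 123 mL | 195 mL | 312 mL |
|---|---|---|---|
| 6 | 117 | 186 | 297 |
| 20 | 263 | 417 | 667 |
| 28 | 317 | 503 | 805 |

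(SD thresholds in mL.) The documents give neither the SD nor a Part B sample size, so this cannot be taken further.

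**Is there an off-drug visit that would show the growth trend?** Not a clean one. SAP 2.1 says "Patients will not have returned to their pre-mepolizumab treatment baseline at the start of part B" (Week 20). Protocol 2.2.2 gives a "terminal-phase elimination half-life of approximately 20 days". By simple decay from the last dose, Week 16 (56 days, 2.8 half-lives) leaves 14.4%, and Weeks 20 and 80 (84 days, 4.2 half-lives) leave 5.4%. Week 80 also covers only some of the children.

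**The case against.** The strongest reply has four parts.

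1. **The shell is unseen.** Table 2.31 borrows another study's layout, which may already carry percent predicted. This stands as a limit on certainty, and the fix allows for it.
2. **No planned conclusion rests on this table.** Part B FEV1 is not an endpoint in the protocol or in SAP 2.2.2, protocol 9.5 plans no Part B FEV1 analysis, Part B has no FEV1 figure, and nothing is tested. Protocol 7.6 says spirometry is done so that the ACQ-7 can be completed, and there FEV1 already enters as percent predicted. This stands too, and keeps the point minor. Even so, SAP Table 7 lists the summary as exploratory, and Table 2.31 will print a CI around a change that includes growth.
3. **The size is wholly external, and the off-drug argument is indirect.** The SAP's remark on Week 20 is attached to eosinophils, ACQ-7 and C-ACT, and the residual fractions describe drug concentration, not effect on FEV1. Both are fair. The concern needs only the direction of the drift, and Week 80 would still cover only part of the group.
4. **Visit height may not exist.** Neither Time and Events table has a height row, protocol 7.2.4 covers pulse and blood pressure, and the ACQ-7 item is recorded in categories, so continuous percent predicted need not be in the database. This stands, and it decides which version of the fix is possible.

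**Conclusion.** The concern holds as a minor reporting weakness. As written, Table 2.31 gives a simple difference from Week 0 out to Week 72 or 80, in uncontrolled growing children, with no height or age standardisation assigned. If the scale is volume, the mean change is biased upwards as a measure of lung-function gain. On the assumptions above, the bias is roughly 120 to 310 mL at Week 72 (central 195 mL, 12%), or about half that if growth in lung function is impaired. At Week 12, where the protocol places its FEV1 endpoint, it is about 2% in the central case and matters little. Confidence is medium, because the unit and shell cannot be seen and the size rests on outside assumptions.

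**What to change.** In SAP 8.1.5 and Table 2.31, and in Table 2.18 for consistency:
- Keep raw FEV1 and state its unit.
- Add change from baseline in GLI-2012 percent predicted or z-score, using height and age at each visit.
- Footnote that raw change from Week 0 includes growth.

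If height was not recorded at the spirometry visits, add only the footnote. Percent predicted should not be computed from baseline height, because that would leave the effect of height growth in the result. If the borrowed shell already has a percent-predicted row, say so in SAP 8.1.5 and add only the footnote.

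The cost is one set of rows, a footnote and a check on what height data exist. The BMI derivation implies that height was captured at least once, and ACQ-7 scoring already needs percent predicted at these visits. Age will be approximate, since only year of birth is collected and 30 June is imputed. That error is fixed within a child, so it affects change less than level.
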